5.2 Type 1 Error Control for Multiple Tests

In order to minimize the impact of multiplicity in this dose-response study, a gatekeeping procedure will be followed to conduct the following analyses in a hierarchical order:

- 1. Primary (SANDE) high concentration vs. vehicle
- 2. Primary (SANDE) middle concentration vs. vehicle
- 3. Primary (SANDE) low concentration vs. vehicle

The comparisons will be conducted at $\alpha = 0.05$. Each comparison will be made in order until p > (exceeds) 0.05. If p ≤ 0.05, the comparison is statistically significant and testing is continued.

5.3 Handling of Missing Data

For efficacy analyses, use of a mixed model for repeated measures (MMRM) approach requires only that data are missing at random so that no other method will be employed to deal with missing data. It may be necessary to test whether this assumption applies to the data set. For sensitivity analysis the last observation carried forward (LOCF) will be used for missing data imputation.

5.4 Methods of Efficacy Analysis

Each endpoint will be summarized for each visit where that endpoint is assessed. Where appropriate, the change from baseline value will be used to assess the difference between each concentration of SDP-4 and vehicle.

Change from baseline endpoints will be analyzed using MMRM analysis with terms for baseline measurement, treatment, visit, and treatment-by-visit interaction. An unstructured variance-covariance matrix will be employed to account for within subject correlation in the repeated measures. In case of model non-convergence a simpler variance-covariance matrix will be employed. Within treatment estimate of least square mean change from baseline and associated standard error will be provided by visit. Also, estimate of difference in least square means of change from baseline between each SDP-4 group and Vehicle (i.e. the estimand) and associated standard error and 95% confidence interval will be provided by visit.

The MMRM analysis is based on a standard linear mixed model, defined as:

$$Y = \mu + B_i + T_t + V_j + TV_{tj} + \underline{\varepsilon_{itj}}$$

Where **Y** denotes an outcome variable, μ is the overall mean, B_i is the baseline value, T_t is the fixed effect due to tth treatment group, V_j is the fixed effect due to the jth visit, TV_{tj} is the treatment by visit interaction, and $\underline{\varepsilon_{itj}}$ is the measurement error associated with the individual subject.

Following is a sample SAS code for MMRM analysis:

proc sort data=datain; by subject_id visit; ods select diffs lsmeans; proc mixed data=datain method=reml; class subject_id treat visit; model cfb_var= baseline treat visit visit*treat / solution rcorr; repeated visit / type=un subject=subject_id rcorr; lsmeans visit*treat / pdiff; run; guit;

For variables with only one post-baseline assessments (e.g. Schirmer's test), change from baseline will be analyzed utilizing analysis of covariance (ANCOVA) with terms for baseline measurement and treatment. The mathematical form of the ANCOVA model is also based on a standard linear mixed model, defined as:

$Y = \mu + B_i + T_t + \underline{\varepsilon_{it}}$

Where **Y** denotes an outcome variable, μ is the overall mean, B_i is the baseline value, T_t is the fixed effect due to tth treatment group, and $\underline{s_{it}}$ is the measurement error associated with the individual subject.

Following is a sample SAS code for ANCOVA analysis:

proc sort data=datain; by subject_id; ods select diffs lsmeans; proc mixed data=datain method=reml; class treat;

model cfb_var= baseline treat / solution rcorr; Ismeans treat / pdiff; run; quit;

5.5 Approaches to Efficacy Analyses

The following table describes detailed approaches to analyze each specific efficacy endpoint.

Table 4. Summary of efficacy analyses

Endpoint	Туре	Statistical Method	Population (Eye)	Missing Data Handling
Mean change from	Primary	MMRM	ит	MMRM
score at Visit 7/Day 84	Supportive	MMRM	PP	MMRM
baseline visits in the analysis)	Sensitivity	MMRM	ІТТ	LOCF
Mean change from baseline at each visit for TBUT (including all post- baseline visits in the analysis)	Secondary	MMRM	ITT (SE&NE)	MMRM
Mean change from baseline at each visit for conjunctival lissamine green staining (combined and each zone)	Secondary	MMRM	ITT (SE&NE)	MMRM
Mean change from baseline at each visit for corneal fluorescein staining (combined and each zone)	Secondary	MMRM	ITT (SE&NE)	MMRM
Mean change from baseline at Day 84 for Schirmer's test	Secondary	ANCOVA	ITT (SE&NE)	No imputation
Mean change from baseline at each visit for conjunctival hyperemia	Secondary	MMRM	ITT (SE&NE)	MMRM

Mean change from baseline at each visit for Individual symptom VAS scores, separately for each symptom	Secondary	MMRM	ITT	MMRM
Mean change from baseline in SANDE severity score at each visit	Secondary	MMRM	ITT	MMRM
Mean change from baseline in SANDE frequency score at each visit	Secondary	MMRM	ІТТ	MMRM

Note: SE = Study Eye, NE = Non-Study Eye

Downloaded by [name] on 4/29/2020

6 SAFETY

All safety parameters will be summarized based on the actual treatment group based on the Safety Population. Subject is the unit of analysis for all safety variables. Subject-level data will be generated for eye-specific safety variables as described below.

6.1 Adverse Events

Treatment-emergent adverse events (TEAEs) are those with onset after randomization or if occurring prior to randomization, worsened after randomization. Only treatment-emergent events will be summarized. All events in the clinical database regardless of when they occurred will be provided in data listings. Adverse events will be classified according to the MedDRA to the levels of System Organ Class (SOC) and primary Preferred Term (PT).

Run-in AEs that occurred during the run-in **period on vehicle** (Note: subjects may be on run-in vehicle for up to 16 days, but **no less than** 12 days) will be summarized separately.

An overall summary will be presented which gives the number and percentage of subjects that experienced any TEAE, experienced any treatment related TEAE, permanently discontinued treatment due to a TEAE, interrupted treatment due to a TEAE, experienced a treatment emergent SAE, and that died.

The number and percentage of subjects experiencing one or more events will be tabulated separately for ocular AEs and non-ocular AEs by SOC and PT. In addition similar tables by SOC and PT will be displayed further by maximum severity, and by closest relationship to treatment.

In summary tables for ocular adverse events, AEs occurring in both eyes will be summarized once at the greater severity or closer relationship to study drug.

The number of and percentage of subjects experiencing AEs leading to premature discontinuation from the study will be tabulated and listed.

A listing of serious TEAEs will be also provided.

A glossary listing that shows the verbatim terms assigned to each SOC and PT will be provided.

6.2 Visual Acuity

Descriptive statistics of the observed and change from baseline BCVA expressed as equivalent logMAR will be tabulated for each eye (study eye and non-study eye) by visit. In addition, the number and percentage of subjects with $a \ge 3$ -line decrease from baseline in BCVA will be tabulated for each eye (study eye and non-study eye) by visit and at any visit.

6.3 Intraocular Pressure

Descriptive statistics of the observed and change from baseline IOP will be tabulated for each eye (study eye and non-study eye) by visit. In addition, the number and percentage of subjects with \geq 10 mmHg increase from baseline in IOP will be tabulated for each eye (study eye and non-study eye) by visit and at any visit.

6.4 Slit-Lamp Examination

Observed results will be summarized for each anterior ocular structure (Lid, Conjunctiva, Cornea, Anterior chamber, Iris/Pupil, Lens status) in frequency tables for each eye (study eye and non-study eye) by visit.

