9.6.2. Safety Analysis

Safety and IP comfort data will be presented in tables of descriptive statistics and frequency distribution. All summary tables will be supported with individual subject data listings.

AEs that occur during the screening/run-in period (Visit 1/Day-14 \pm 2 to Visit 2/Day 1) will be summarized separately from AEs that occur from the first dose of double-masked treatment on Day 1 to the Day 56 Visit or Early Discontinuation.

The primary safety analysis will summarize ocular and non-ocular treatment-emergent adverse events (TEAEs) using discrete summaries at the subject level by system organ class and preferred term for each treatment group. A TEAE will be defined as occurring after the first dose of IP. Serious adverse events (SAEs) and treatment-related ocular and non-ocular TEAEs will be summarized similarly. Ocular and non-ocular TEAEs will also be summarized by severity.

Biomicroscopy and dilated indirect ophthalmoscopy measures will be summarized by tabulating the distribution of score shifts between baseline and post-baseline assessments

Best-corrected visual acuity (BCVA; logMAR) will be summarized at each visit, using continuous and discrete summary statistics, including change from baseline and the proportion of study eyes with pre-defined increases from baseline, specifically, eyes with a 3-line decrease in BCVA.

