1 INTRODUCTION

This statistical analysis plan (SAP) describes the final statistical analysis for subject information, efficacy data, and safety data to be done for the study entitled "A Phase 2, Multicenter, Double-Masked, Randomized, Vehicle-Controlled, Parallel-Group, Dose-Response Study of SDP-4 Ophthalmic Solution in Subjects with Dry Eye Disease (DED)" (Date Amendment 1: 03APR2019). Mock shells are also produced as a separate working document to facilitate programming of Tables, Figures, and Listings (TFLs) according to finalized SAP. The SAP is to be interpreted in conjunction with the protocol, and supersedes the statistical considerations identified in the protocol. If the final clinical study report (CSR) contains changes to any planned statistical analyses, the justification for any such differences will be fully documented in the CSR.

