2.5 Out of Window and Unscheduled Visits

All scheduled assessments after first administration of randomized IP will be used. The protocol defined windows for scheduled visits will not be used in the analyses by visit. Data will be assigned to the scheduled visit closer in time to the scheduled visit. Unscheduled visit data will only be used in an analysis if there is no other available data closer in time to a scheduled visit. Post first dose unscheduled assessments will be taken into account for worst-case determination as applicable. All unscheduled visit data will be included in data listings.

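### The SAP's slit-lamp tables show only observed frequencies by eye and visit: they do not match the protocol's shifts from baseline and have no any-visit or worst-value summary

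*SAP*

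**What the plan says.** SAP 6.4 contains one rule: "Observed results will be summarized for each anterior ocular structure (Lid, Conjunctiva, Cornea, Anterior chamber, Iris/Pupil, Lens status) in frequency tables". The sentence ends "in frequency tables for each eye (study eye and non-study eye) by visit". The SAP's list of tables has two matching entries, 14.3.5.1 (study eye) and 14.3.5.2 (non-study eye), both titled as results. No shift or categorized-change table is listed for the slit lamp.

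Protocol 9.6.2 says biomicroscopy will be "summarized by tabulating the distribution of score shifts between baseline and post-baseline assessments".

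The neighbouring SAP sections go further than 6.4. In SAP 6.2, acuity gets observed values, change from baseline and a threshold count that "will be tabulated for each eye (study eye and non-study eye) by visit and at any visit". SAP 6.3 does the same for pressure: "Descriptive statistics of the observed and change from baseline IOP will be tabulated for each eye (study eye and non-study eye) by visit", plus a threshold count by visit and at any visit.

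Two general SAP rules also bear on the point. SAP 2.5 uses an unscheduled examination in a by-visit analysis only when no other data lie closer to the scheduled visit, and adds: "Post first dose unscheduled assessments will be taken into account for worst-case determination as applicable". SAP 6 states: "Subject-level data will be generated for eye-specific safety variables as described below".

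**The concern.** Safety is part of the primary objective (Protocol 2.1), and the slit lamp is one of the few objective ocular safety examinations for this topical drop. The safety question is how many eyes develop a finding, or worsen, after starting treatment. A by-visit frequency answers a different question: how many eyes have the finding on that day. It mixes long-standing, new and resolved findings, and it cannot be added across visits to give the number ever affected.

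SAP 2.5 provides for a worst-case determination, but SAP 6.4 defines no worst-case slit-lamp summary for that provision to feed. If 6.4 is carried into the CS202 SAP unchanged, the shifts planned in Protocol 9.6.2 will have no table.

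**Working it through.** The documents give no figure to reproduce here. The check compares the passages and then illustrates the effect with assumed counts.

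**Comparison of the rules**

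| Source | Change from baseline | Any-visit or worst value |
|---|---|---|
| Protocol 9.6.2, biomicroscopy | Yes, score shifts | Not specified |
| SAP 6.4 and Tables 14.3.5.1/14.3.5.2 | No | No |
| SAP 6.2, visual acuity | Yes | Yes, any visit |
| SAP 6.3, intraocular pressure | Yes | Yes, any visit |

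SAP 2.9 does not fill the gap: for categorical endpoints it gives counts and percentages at scheduled visits, with no shift rule. The data would support shifts. SAP Table 3 records negative/positive results by structure, grades of 0-3 (such as lid erythema and edema) or 0-4 (such as cells and flare), and clinical significance.

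**Netting within an arm.** Take n = 70 eyes per arm (Protocol 9.1). The other counts are assumptions: B positive at baseline, R resolved, N new.

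- Frequency in the 6.4 table = (B − R + N)/n
- New-onset rate in a shift table = N/(n − B)

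With B = 10, R = 6, N = 6, the baseline row is 10/70 = 14.3% and the visit row is (10 − 6 + 6)/70 = 14.3%. The shift table gives 6/(70 − 10) = 6/60 = 10.0% new onset.

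The range with R = N is:

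| B | N | 6.4 table, both times | New onset |
|---|---|---|---|
| 7 | 3 | 7/70 = 10.0% | 3/63 = 4.8% |
| 7 | 7 | 7/70 = 10.0% | 7/63 = 11.1% |
| 14 | 3 | 14/70 = 20.0% | 3/56 = 5.4% |
| 14 | 7 | 14/70 = 20.0% | 7/56 = 12.5% |

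**Cumulative incidence.** Suppose each post-baseline row shows 2/70 = 2.9%. Over the protocol's three on-treatment visits, the number ever affected lies between 2 (the same subjects each time) and 2 × 3 = 6 (different subjects), that is 2.9% to 8.6%. Over the five visits in the SAP supplied, the upper limit is 2 × 5 = 10, or 14.3%. The by-visit rows cannot tell these cases apart.

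**Unscheduled examinations.** If a finding is seen only at an unscheduled visit and scheduled data lie closer in time, SAP 2.5 keeps it out of the by-visit row. It then counts as 0 in both slit-lamp tables and appears only in a listing.

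**Comparison with vehicle.** Assume 7/70 positive at baseline in each arm and no change on vehicle. If the drug causes 7 findings and resolves none, the visit rows read 14/70 = 20.0% against 7/70 = 10.0%, so the harm shows. If it causes 7 and resolves 7, both arms read 10.0%, while new onset is 7/63 = 11.1% against 0/63.

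**The case against.** The strongest objection concerns which study the SAP belongs to. It is Final Version 1.0 of 24 June 2019, written against a protocol amendment dated 03APR2019, with four arms, 84 days and seven visits. The protocol is dated 06 March 2020, with two arms, 56 days and five visits. A reader might infer from SAP 1, which says that the SAP "supersedes the statistical considerations identified in the protocol", that the protocol's shift analysis has been validly replaced. The documents do not support that: a SAP finalised more than eight months earlier refers to a different protocol. Nor can SAP 8, which lists no such change, be read as an undisclosed departure, because the protocol it was compared with is not available. The only slit-lamp analysis text written for CS202 is Protocol 9.6.2, which already asks for shifts. This objection stands and limits the point to a conflict to resolve.

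A reader might also infer that the planned output cannot show worsening on treatment at all. That is too strong:

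- Under Protocol 6.4.1.1, abnormal results that are clinically significant, cause signs or symptoms, or need therapy are adverse events. SAP 6.1 tabulates ocular treatment-emergent events by subject, including worsening after randomization.
- Hyperemia and corneal staining have change-from-baseline models in both eyes (SAP Table 4).
- Listing 16.2.8.3 gives slit-lamp results, and all unscheduled data are listed.
- The vehicle arm shows net harm, as in the last calculation. Complete masking needs the drug to resolve about as many findings as it causes.
- A finding present at a scheduled visit is counted in that row.

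What survives is narrower. Findings judged not clinically significant need not become adverse events, and Protocol 6.6 says disease-related changes from baseline will not necessarily be recorded as such. The efficacy models give mean changes and do not cover lid erythema, edema, cells or flare.

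Finally, the lack of an either-eye count is not particular to 6.4, since acuity and pressure are also tabulated by eye. The subject-level statement in SAP 6 is met at least for ocular adverse events in 6.1.

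**Conclusion.** The point holds as a mismatch and an inexpensive improvement. SAP 6.4 gives by-visit prevalence only, Protocol 9.6.2 plans shifts from baseline, and the SAP's own treatment of acuity and pressure is fuller. Carried into a CS202 SAP, the 6.4 wording would hide new onset where it is offset by resolution, leave cumulative incidence unreadable, and keep some unscheduled-only findings out of the slit-lamp tables. The affected information is mainly findings that are not recorded as adverse events.

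The size cannot be estimated from the documents, which give no slit-lamp rates. The illustrated gaps (new onset of 4.8% to 12.5% behind an unchanged row; up to 8.6% ever affected behind 2.9% per visit over three visits) rest on assumed counts, and the netting examples assume equal numbers new and resolved. The conclusion also assumes that the CS202 case report form keeps the grading in SAP Table 3. Protocol 9.6.2 refers to scores but does not list the grades.

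**What to change.** When the CS202 SAP is finalised, bring 6.4 into line with Protocol 9.6.2. Suggested wording:

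> For each graded or negative/positive slit-lamp finding, and for each eye, shift tables by treatment group will be presented from baseline to each scheduled visit and from baseline to the worst post-baseline result. The worst result will include unscheduled and early-termination examinations. Lens status and other ungraded findings will be summarized in frequency tables by visit.

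Change Tables 14.3.5.1 and 14.3.5.2 accordingly. The worst-value shift supplies the any-visit summary and gives the worst-case provision in SAP 2.5 something to act on. Lens status and ungraded findings stay as frequencies because they have no ordered scale. A count of subjects with worsening in either eye is optional.

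The cost is SAP wording and a small amount of extra table programming. No new data, visits or subjects are needed.

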6.5 Dilated Fundus Examination

Observed results will be summarized for each structure (i.e. vitreous, optic nerve, macula, peripheral retina, cup-to disc ratio) in frequency tables for each eye (study eye and non-study eye) by visit.

7 OTHER ASSESSMENT

IP comfort assessment results will be summarized in a frequency table by visit.

8 CHANGES FROM PROTOCOL

- Following analyses have been removed from hierarchy of analyses as described in protocol Section 9.5.3 Efficacy analysis:
 - Secondary (TBUT) high concentration vs. vehicle
 - Secondary (TBUT) middle concentration vs. vehicle
 - Secondary (TBUT) low concentration vs. vehicle
- IP comfort assessment has been disregarded as one of the safety assessments.

Downloaded by [name] on 4/29/2020

REFERENCES

None

Statistical Analysis Plan: Final Version 1.0, 24 June 2019

Downloaded by [name] on 4/29/2020

9 TABLES, LISTING, FIGURES

9.1 List of Tables

Table Number	Table Title	Study Population
14.1.1	Analysis Populations	ITT
14.1.2.1	Subject Disposition	ITT
14.1.2.2	Subject Disposition by Site	ITT
14.1.3	Visit Participation	ITT
14.1.4	Demographics	ITT
14.1.5.1	Medical History	ITT
14.1.5.2	Ocular History	ITT
14.1.6.1	Prior Medications (Ocular and Non-ocular)	SAF
14.1.6.2	Concomitant Medications (Ocular and Non-ocular)	SAF
14.1.7.1	Treatment Exposure	SAF
14.1.7.2	Treatment of Artificial Tears	SAF
14.1.8.1	Major Protocol Deviations	ITT
14.1.8.2	Inclusion and Exclusion Exceptions	ITT
14.2.1.1.1	Mean Change from Baseline in Total SANDE Score	ITT
14.2.1.1.2	Mean Change from Baseline in Total SANDE Score	PP
14.2.1.1.3	Mean Change from Baseline in Total SANDE Score (LOCF)	ITT
14.2.1.2.1	Mean Change from Baseline in SANDE Severity Score	ITT
14.2.1.2.2	Mean Change from Baseline in SANDE Severity Score	PP
14.2.1.3.1	Mean Change from Baseline in SANDE Frequency Score	ITT
14.2.1.3.2	Mean Change from Baseline in SANDE Frequency Score	PP
14.2.2.1	Mean Change from Baseline in Tear Break-up Time - Study Eye	ITT
14.2.2.2	Mean Change from Baseline in Tear Break-up Time - Non-Study Eve	ITT
14.2.3	Mean Change from Baseline in Individual Symptom VAS Scores	ITT
14.2.4.1	Mean Change from Baseline in Conjunctival Lissamine Green	ITT
	Staining - Study Eye	
14.2.4.2	Mean Change from Baseline in Conjunctival Lissamine Green Staining - Non-Study Eve	ITT
14.2.5.1	Mean Change from Baseline in Corneal Fluorescein Staining -	ITT
14.2.5.2	Mean Change from Baseline in Corneal Fluorescein Staining -	ITT
14.2.6.1	Mon-Study Eye Mean Change from Baseline in Conjunctival Hyperemia - Study	ITT
14.2.6.2	Mean Change from Baseline in Conjunctival Hyperemia - Non- Study Eve	ITT
14.2.7.1	Mean Change from Baseline in Schirmer's Test - Study Eve	ITT
14.2.7.2	Mean Change from Baseline in Schirmer's Test - Non-Study Eve	ITT
14.3.1.1	Summary of Treatment-Emergent Adverse Events	SAF
14.3.1.2.1	Frequency of Ocular Treatment-Emergent Adverse Events by	SAF
	System Organ Class and Preferred Term	
14.3.1.2.2	Frequency of Non-Ocular Treatment-Emergent Adverse Events by System Organ Class and Preferred Term	SAF

.

14.3.1.3.1	Frequency of Ocular Treatment-Emergent Adverse Events by System Organ Class and Preferred Term and by Maximum	SAF
14.3.1.3.2	Severity Frequency of Non-Ocular Treatment-Emergent Adverse Events by System Organ Class and Preferred Term and by Maximum	SAF
14.3.1.4.1	Frequency of Ocular Treatment-Emergent Adverse Events by System Organ Class and Preferred Term and by Closest Relatedness	SAF
14.3.1.4.2	Frequency of Non-Ocular Treatment-Emergent Adverse Events by System Organ Class and Preferred Term and by Closest Relatedness	SAF
14.3.1.5.1	Frequency of Ocular Treatment-Emergent Adverse Events Leading to Permanent Withdrawal of Study Medication by System Organ Class and Preferred Term	SAF
14.3.1.5.2	Frequency of Non-Ocular Treatment-Emergent Adverse Events Leading to Permanent Withdrawal of Study Medication by System Organ Class and Preferred Term	SAF
14.3.1.6.1	Frequency of Ocular Run-in Adverse Events by System Organ Class and Preferred Term	SAF
14.3.1.6.2	Frequency of Non-Ocular Run-in Adverse Events by System Organ Class and Preferred Term	SAF
14.3.1.7	Adverse Event - MedDRA Glossary	SAF
14.3.2	Listing of Serious Treatment Emergent Adverse Events	SAF
14.3.3.1	Mean Change from Baseline in Visual Acuity - Study Eye	SAF
14.3.3.2	Categorized Change from Baseline in Visual Acuity - Study Eye	SAF
14.3.3.3	Mean Change from Baseline in Visual Acuity - Non-Study Eye	SAF
14.3.3.4	Categorized Change from Baseline in Visual Acuity - Non-Study Eye	SAF
14.3.4.1	Mean Change from Baseline in Intraocular Pressure - Study Eye	SAF
14.3.4.2	Categorized Change from Baseline in Intraocular Pressure - Study Eve	SAF
14.3.4.3	Mean Change from Baseline in Intraocular Pressure - Non-Study Eye	SAF
14.3.4.4	Categorized Change from Baseline in Intraocular Pressure - Non- Study Eye	SAF
14.3.5.1	Slit-Lamp Examination Results - Study Eye	SAF
14.3.5.2	Slit-Lamp Examination Results - Non-Study Eye	SAF
14.3.6.1	Dilated Fundus Examination Results - Study Eye	SAF
14.3.6.2	Dilated Fundus Examination Results - Non-Study Eye	SAF
14.3.7	Investigational Product Comfort Assessment	SAF

Listing		Study
Number	Listing Title	Population
16.1.7	Randomization	ITT
16.2.1.1	Screen Failures	SCRN
16.2.1.2	Subject Disposition	ITT
16.2.1.3	Analysis Visits	ITT
16.2.2.1	Inclusion and Exclusion Criteria Exceptions	ITT
16.2.2.2	Protocol Deviations	ITT
16.2.3	Analysis Populations	ITT
16.2.4.1	Demographics	ITT
16.2.4.2.1	Significant Medical History	ITT
16.2.4.2.2	Significant Ocular History	ITT
16.2.4.3.1	Prior Ocular Medications	SAF
16.2.4.3.2	Concomitant Ocular Medications	SAF
16.2.4.3.3	Prior Non-Ocular Medications	SAF
16.2.4.3.4	Concomitant Non-Ocular Medications	SAF
16.2.5.1	Run-In Exposure	SAF
16.2.5.2	Run-In Medication Dispensation and Return	SAF
16.2.5.3	Treatment Exposure	SAF
16.2.5.4	Treatment Medication Dispensation and Return	SAF
16.2.5.5	Artificial Tears	SAF
16.2.6.1	SANDE Symptom Score	ITT
16.2.6.2	Tear Break-up Time	ITT
16.2.6.3	Individual Symptom VAS Scores	ITT
16.2.6.4	Conjunctival Lissamine Green Staining Results	ITT
16.2.6.5	Corneal Fluorescein Staining Results	ITT
16.2.6.6	Conju nctival Hype remia Results	ITT
16.2.6.7	Schirmer's Test Results	ITT
16.2.7.1	Treatment Emergent Adverse Events	SAF
16.2.7.2	Run-in Adverse Events	SAF
16.2.8.1	Visual Acuity	SAF
16.2.8.2	Intraocular Pressure	SAF
16.2.8.3	Slit-Lamp Examination	SAF
16.2.8.4	Dilated Fundus Examination	SAF
16.2.8.5	Investigational Product Comfort Assessment	SAF
16.2.8.6	Urine Pregnancy Test	SAF
16.2.8.7	General Comments	SAF

